# 10 ADVERSE EVENTS: LIST AND REPORTING REQUIREMENTS

AE monitoring and reporting is a routine part of every clinical trial. The following list of AEs (Section 10.1) and the characteristics of an observed AE (Sections 10.2 and 10.3) will determine whether the event requires expedited reporting via the CTEP Adverse Event Reporting System (CTEP-AERS) in addition to routine reporting.

# 10.1 Comprehensive Adverse Events and Potential Risks List(s) (CAEPRs)

The Comprehensive Adverse Events and Potential Risks list (CAEPR) provides a single list of reported and/or potential adverse events (AE) associated with an agent using a uniform presentation of events by body system. In addition to the comprehensive list, a subset, the Specific Protocol Exceptions to Expedited Reporting (SPEER), appears in a separate column and is identified with bold and italicized text. This subset of AEs (SPEER) is a list of events that are protocol specific exceptions to expedited reporting to NCI (except as noted below). Refer to the 'CTEP, NCI Guidelines: Adverse Event Reporting Requirements' http://ctep.cancer.gov/protocolDevelopment/electronic\_applications/docs/aeguidelines.pdf for further clarification.

**NOTE:** Report AEs on the SPEER ONLY IF they exceed the grade noted in parentheses next to the AE in the SPEER. If this CAEPR is part of a combination protocol using multiple investigational agents and has an AE listed on different SPEERs, use the lower of the grades to determine if expedited reporting is required.

# **10.1.1** CAEPRs for CTEP IND Agent(s)

#### 10.1.1.1 CAEPRs for Hu5F9-G4 (magrolimab), NSC 809249

Below is the CAEPR for Hu5F9-G4 (magrolimab). Frequency is based on 1328 patients.

Version 2.2, December 6, 2023 **Adverse Events with Possible** Relationship to Hu5F9-G4 (Magrolimab) **Specific Protocol Exceptions to** (CTCAE 5.0 Term) Expedited Reporting (SPEER) [n=1328]Likely (>20%) Less Likely (<=20%) Rare but Serious (<3%) BLOOD AND LYMPHATIC SYSTEM DISORDERS Anemia (Gr 2) Anemia Blood and lymphatic system disorders - Other (red blood cell agglutination) Febrile neutropenia Febrile neutropenia (Gr 2) Hemolysis GASTROINTESTINAL DISORDERS Abdominal pain (Gr 2) Abdominal pain Diarrhea Diarrhea (Gr 2) Nausea (Gr 2) Nausea Vomiting Vomiting (Gr 2) GENERAL DISORDERS AND ADMINISTRATION SITE CONDITIONS Chills (Gr 2) Chills Fatigue Fatigue (Gr 2) Fever Fever (Gr 2) Generalized edema INFECTIONS AND INFESTATIONS Lung infection Sepsis INJURY, POISONING AND PROCEDURAL COMPLICATIONS Infusion related reaction Infusion related reaction (Gr 2) INVESTIGATIONS Blood bilirubin increased Blood bilirubin increased (Gr 2) Lymphocyte count decreased Lymphocyte count decreased (Gr 2) Neutrophil count decreased Neutrophil count decreased (Gr 2) Platelet count decreased Platelet count decreased (Gr 2) White blood cell decreased White blood cell decreased (Gr 2) METABOLISM AND NUTRITION DISORDERS Anorexia (Gr 2) Anorexia Hypokalemia Hypokalemia (Gr 2) MUSCULOSKELETAL AND CONNECTIVE TISSUE DISORDERS Arthralgia Back pain NERVOUS SYSTEM DISORDERS Dizziness Headache (Gr 2) Headache RESPIRATORY, THORACIC AND MEDIASTINAL DISORDERS

Rel	Specific Protocol Exceptions to Expedited Reporting (SPEER)		
Likely (>20%)	Less Likely (<=20%)	Rare but Serious (<3%)	
	Cough		
	Dyspnea		
SKIN AND SUBCUTANEOU	S TISSUE DISORDERS		
VASCULAR DISORDERS			
Hypotension			

This table will be updated as the toxicity profile of the agent is revised. Updates will be distributed to all Principal Investigators at the time of revision. The current version can be obtained by contacting [contact]. Your name, the name of the investigator, the protocol and the agent should be included in the e-mail.

Adverse events reported on Hu5F9-G4 (Magrolimab) trials, but for which there is insufficient evidence to suggest that there was a reasonable possibility that Hu5F9-G4 (Magrolimab) caused the adverse event:

BLOOD AND LYMPHATIC SYSTEM DISORDERS - Thrombotic thrombocytopenic purpura

GASTROINTESTINAL DISORDERS - Colitis; Constipation; Mucositis oral; Small intestinal obstruction

GENERAL DISORDERS AND ADMINISTRATION SITE CONDITIONS - Pain

**IMMUNE SYSTEM DISORDERS - Serum sickness** 

INFECTIONS AND INFESTATIONS - Conjunctivitis; Urinary tract infection

**INVESTIGATIONS** - Alkaline phosphatase increased; Aspartate aminotransferase increased

METABOLISM AND NUTRITION DISORDERS - Hypomagnesemia; Hypophosphatemia

MUSCULOSKELETAL AND CONNECTIVE TISSUE DISORDERS - Pain in extremity

NEOPLASMS BENIGN, MALIGNANT AND UNSPECIFIED (INCL CYSTS AND POLYPS) - Tumor pain

**NERVOUS SYSTEM DISORDERS** - Edema cerebral; Intracranial hemorrhage; Nervous system disorders - Other (cerebral hemorrhage)

RESPIRATORY, THORACIC AND MEDIASTINAL DISORDERS - Epistaxis; Hypoxia; Pneumonitis SKIN AND SUBCUTANEOUS TISSUE DISORDERS - Dry skin; Rash acneiform; Rash maculo-papular

VASCULAR DISORDERS - Hypertension; Thromboembolic event

**Note**: Hu5F9-G4 (Magrolimab) in combination with other agents could cause an exacerbation of any adverse event currently known to be caused by the other agent, or the combination may result in events never previously associated with either agent.

# 10.1.1.2 CAEPR for Dinutuximab (MoAb 14.18 chimeric (CH14.18)), NSC 764038

Below is the CAEPR for Dinutuximab (MoAb 14.18 chimeric (CH14.18)). Frequency is based on 359 patients.

			Version 2.9, January 10, 2019 
Relation	Specific Protocol Exceptions to Expedited Reporting (SPEER)		
Likely (>20%)	Less Likely (<=20%)	Rare but Serious (<3%)	
BLOOD AND LYMPHATIC	SYSTEM DISORDERS		
	Anemia		Anemia (Gr 3)
	Disseminated intravascular coagulation		Disseminated intravascular coagulation (Gr 2)
		Hemolytic uremic syndrome 	
CARDIAC DISORDERS			
		Cardiac arrest	
		Sinus bradycardia	
	Sinus tachycardia		Sinus tachycardia (Gr 3)
EYE DISORDERS			
		Eye disorders - Other (eye disorders) 	
GASTROINTESTINAL DISC	ORDERS		
	Abdominal pain		Abdominal pain (Gr 3)
	Diarrhea		Diarrhea (Gr 3)
	Nausea		Nausea (Gr 2)
	Vomiting		Vomiting (Gr 3)
GENERAL DISORDERS AN	ND ADMINISTRATION SITE (	CONDITIONS	
	Edema limbs		Edema limbs (Gr 2)
Fever			Fever (Gr 3)
	Generalized edema		
Pain			Pain (Gr 3)
		Sudden death NOS	,
IMMUNE SYSTEM DISORD	DERS		
	Allergic reaction		Allergic reaction (Gr 3)
	7 m.e.g.e : ed.eu.e	Anaphylaxis	
	Serum sickness	, and projection	
INFECTIONS AND INFEST			
IN ECTIONS AND IN ECT	Infection 		Infection  (Gr 3)
	Integration	Myelitis 	inceden (Gr 5)
INJURY POISONING AND	PROCEDURAL COMPLICAT		
INCORT, POISONNO AND		Infusion related reaction	
INVESTIGATIONS		Thradion related reaction	
INVESTIGATIONS	Alanine aminotransferase		Alanine aminotransferase increased
	increased		(Gr 3)
	Aspartate aminotransferase increased		Aspartate aminotransferase increased (Gr 3)
	Creatinine increased		Creatinine increased (Gr 2)
Investigations - Other (elevated c-reactive proteins)			Investigations - Other (elevated c- reactive proteins) (Gr 2)
	Lymphocyte count decreased		Lymphocyte count decreased (Gr 4)

Relatio	Specific Protocol Exceptions to Expedited Reporting (SPEER)		
Likely (>20%)	Less Likely (<=20%)	Rare but Serious (<3%)	
	Neutrophil count decreased		Neutrophil count decreased (Gr 3)
	Platelet count decreased		Platelet count decreased (Gr 4)
	White blood cell decreased		
METABOLISM AND NUTF	RITION DISORDERS		
	Anorexia		Anorexia (Gr 3)
	Hyperkalemia		Hyperkalemia (Gr 2)
	Hypoalbuminemia		Hypoalbuminemia (Gr 3)
	Hypocalcemia		
	Hypokalemia		Hypokalemia (Gr 4)
	Hyponatremia		Hyponatremia (Gr 3)
MUSCULOSKELETAL AN	ID CONNECTIVE TISSUE DISO	RDERS	
	Back pain		Back pain (Gr 3)
	Pain in extremity		,
NERVOUS SYSTEM DISC	ORDERS		
	Neuralgia		Neuralgia (Gr 2)
	J	Peripheral motor neuropathy	
	Peripheral sensory neuropathy 		Peripheral sensory neuropathy  (Gr 3)
		Reversible posterior leukoencephalopathy syndrome	
RENAL AND URINARY D	ISORDERS		
	Proteinuria		Proteinuria (Gr 2)
		Renal and urinary disorders - Other (atonic urinary bladder) 	
	Urinary retention 		
RESPIRATORY, THORAG	CIC AND MEDIASTINAL DISOR	DERS	
	Bronchial obstruction		
Cough			Cough (Gr 3)
	Dyspnea		Dyspnea (Gr 3)
	Hypoxia		Hypoxia (Gr 3)
SKIN AND SUBCUTANEO	OUS TISSUE DISORDERS		
	Pruritus		Pruritus (Gr 2)
Rash maculo-papular			Rash maculo-papular (Gr 2)
	Urticaria		Urticaria (Gr 3)
VASCULAR DISORDERS			
	Capillary leak syndrome		Capillary leak syndrome (Gr 3)
	Hypertension		
	Hypotension		Hypotension (Gr 3)

<sup>1This table will be updated as the toxicity profile of the agent is revised. Updates will be distributed to all Principal Investigators at the time of revision. The current version can be obtained by contacting [contact]. Your name, the name of the investigator, the protocol and the agent should be included in the e-mail.

<sup>2There have been rare instances of atypical hemolytic uremic syndrome in the absence of documented infection and resulting in renal insufficiency, electrolyte abnormalities, anemia, and hypertension.

<sup>3Neurological disorders of the eye including blurred vision, diplopia, cycloplegia, mydriasis, photophobia, optic nerve disorder, eyelid Version Date: 02/02/2024

Page 89

ptosis, and fixed pupils have been observed.

Infection includes all 75 sites of infection under the INFECTIONS AND INFESTATIONS SOC.

Myelitis expressed as transverse myelitis has occurred in patients treated with chimeric MoAb 14.18. Symptoms may include weakness, paresthesia, sensory loss, or incontinence.

Acute urinary retention occurs during therapy and is thought to be due to fluid shifts and narcotic administration that accompany ch14.18 administration. Atonic urinary bladder results in chronic urinary retention (CUR) that requires intermittent urethral catheterization days to weeks following chimeric MoAb 14.18 administration.

Adverse events reported on MoAb 14.18, chimeric (CH14.18) trials, but for which there is insufficient evidence to suggest that there was a reasonable possibility that MoAb 14.18, chimeric (CH14.18) caused the adverse event:

**BLOOD AND LYMPHATIC SYSTEM DISORDERS** - Blood and lymphatic system disorders - Other (thrombotic microangiopathy [e.g., thrombotic thrombocytopenic purpura [TTP] or hemolytic uremic syndrome [HUS]); Bone marrow hypocellular; Febrile neutropenia; Hemolysis

CARDIAC DISORDERS - Cardiac disorders - Other (gallop on exam); Cardiac disorders - Other (N-terminal BNP); Chest pain - cardiac; Heart failure; Left ventricular systolic dysfunction; Mobitz (type) II atrioventricular block; Myocardial infarction; Palpitations; Pericardial effusion; Supraventricular tachycardia; Ventricular tachycardia

EAR AND LABYRINTH DISORDERS - Ear pain; Hearing impaired

**ENDOCRINE DISORDERS** - Endocrine disorders - Other (transient hypoaldosteronism); Hyperthyroidism; Hypothyroidism **EYE DISORDERS** - Papilledema; Periorbital edema; Scleral disorder

GASTROINTESTINAL DISORDERS - Abdominal distension; Ascites; Cheilitis; Colitis; Constipation; Duodenal obstruction; Dysphagia; Enterocolitis; Esophageal stenosis; Esophageal ulcer; Esophagitis; Gastrointestinal disorders - Other (bleeding, NOS); Gastrointestinal disorders - Other (esophageal stricture); Gastrointestinal disorders - Other (ischemic bowel); Gastrointestinal disorders - Other (pneumatosis intestinalis); Gastroparesis; Hemorrhoidal hemorrhage; Ileus; Intra-abdominal hemorrhage; Lower gastrointestinal hemorrhage; Mucositis oral; Oral pain; Rectal hemorrhage; Stomach pain; Typhlitis

**GENERAL DISORDERS AND ADMINISTRATION SITE CONDITIONS** - Chills; Death NOS; Edema face; Edema trunk; Fatigue; General disorders and administration site conditions - Other (cold and clammy); General disorders and administration site conditions - Other (vascular leak syndrome); Hypothermia; Injection site reaction; Localized edema; Non-cardiac chest pain **HEPATOBILIARY DISORDERS** - Hepatobiliary disorders - Other (cholestasis)

IMMUNE SYSTEM DISORDERS - Cytokine release syndrome

INJURY, POISONING AND PROCEDURAL COMPLICATIONS - Fracture

INVESTIGATIONS - Activated partial thromboplastin time prolonged; Alkaline phosphatase increased; Blood bilirubin increased; Cardiac troponin I increased; Cholesterol high; Ejection fraction decreased; Electrocardiogram QT corrected interval prolonged; Fibrinogen decreased; GGT increased; INR increased; Lipase increased; Lymphocyte count increased; Urine output decreased; Weight gain; Weight loss

**METABOLISM AND NUTRITION DISORDERS** - Acidosis; Dehydration; Hypercalcemia; Hyperglycemia; Hypermagnesemia; Hypernatremia; Hypertriglyceridemia; Hypoglycemia; Hypomagnesemia; Hypophosphatemia

MUSCULOSKELETAL AND CONNECTIVE TISSUE DISORDERS - Arthralgia; Arthritis; Bone pain; Chest wall pain; Muscle weakness lower limb; Myalgia; Neck pain

**NERVOUS SYSTEM DISORDERS** - Cognitive disturbance; Depressed level of consciousness; Dysesthesia; Dysgeusia; Dysphasia; Encephalopathy; Extrapyramidal disorder; Headache; Hydrocephalus; Meningismus; Movements involuntary; Nystagmus; Oculomotor nerve disorder; Paresthesia; Seizure; Somnolence; Syncope; Tremor

**PSYCHIATRIC DISORDERS** - Agitation; Anxiety; Confusion; Delirium; Hallucinations; Insomnia; Irritability; Personality change; Restlessness

**RENAL AND URINARY DISORDERS** - Acute kidney injury; Chronic kidney disease; Glucosuria; Hematuria; Renal and urinary disorders - Other (acute renal insufficiency); Renal and urinary disorders - Other (urethritis); Renal hemorrhage

**REPRODUCTIVE SYSTEM AND BREAST DISORDERS** - Hematosalpinx; Ovarian hemorrhage; Pelvic pain; Penile pain; Prostatic hemorrhage; Spermatic cord hemorrhage; Testicular hemorrhage; Uterine hemorrhage; Vaginal hemorrhage

RESPIRATORY, THORACIC AND MEDIASTINAL DISORDERS - Adult respiratory distress syndrome; Apnea; Atelectasis; Bronchospasm; Laryngeal edema; Laryngopharyngeal dysesthesia; Laryngospasm; Pharyngolaryngeal pain; Pleural effusion; Pleuritic pain; Pneumonitis; Pulmonary edema; Respiratory failure; Respiratory, thoracic and mediastinal disorders - Other (tachypnea);

Stridor; Wheezing

SKIN AND SUBCUTANEOUS TISSUE DISORDERS - Dry skin; Erythema multiforme; Hyperhidrosis VASCULAR DISORDERS - Flushing

*Note*: Dinutuximab (MoAb 14.18, chimeric) in combination with other agents could cause an exacerbation of any adverse event currently known to be caused by the other agent, or the combination may result in events never previously associated with either agent.

Magrolimab activates macrophages as does dinutuximab. Given that dinutuximab causes pain due to GD2 expression on normal nerve cells, there is a theoretical potential for worsening of this pain or other neurologic toxicity such as motor dysfunction or permanent damage to peripheral nerve cells.

## 10.2 Adverse Event Characteristics

• CTCAE term (AE description) and grade: The descriptions and grading scales found in the revised NCI Common Terminology Criteria for Adverse Events (CTCAE) version 5.0 will be utilized for AE reporting. All appropriate treatment areas should have access to a copy of the CTCAE version 5.0. A copy of the CTCAE version 5.0 can be downloaded from the CTEP website http://ctep.cancer.gov/protocolDevelopment/electronic applications/ctc.htm.

## • For expedited reporting purposes only:

- AEs for the agent that are **bold and italicized** in the CAEPR (*i.e.*, those listed in the SPEER column, **Section 10.1**) should be reported through CTEP-AERS only if the grade is above the grade provided in the SPEER.
- Other AEs for the protocol that do not require expedited reporting are outlined in Section 10.3.4, if any exist.

## • **Attribution** of the AE:

- Definite The AE *is clearly related* to the study treatment.
- Probable The AE *is likely related* to the study treatment.
- Possible The AE *may be related* to the study treatment.
- Unlikely The AE *is doubtfully related* to the study treatment.
- Unrelated The AE *is clearly NOT related* to the study treatment.

# 10.3 Expedited Adverse Event Reporting

#### **10.3.1** Rave-CTEP-AERS Integration

The Cancer Therapy Evaluation Program Adverse Event Reporting System (CTEP-AERS) integration enables evaluation of post-baseline AEs entered in Rave to determine whether they require expedited reporting and facilitates entry in CTEP-AERS for those AEs requiring expedited reporting.

All AEs that occur after baseline are collected in Medidata Rave using the Adverse Event form, which is available for entry at each treatment or reporting period and used to collect AEs that start during the period or persist from the previous reporting period. The Clinical Research Associate (CRA) will enter AEs that occur prior to the start of treatment on a baseline form that is not included in the Rave-CTEP-AERS integration. AEs that occur prior to enrollment must begin and end on the baseline Adverse Event form and should not be included on the standard Adverse Events form that is available at treatment unless there has been an increase in grade.

Prior to sending AEs through the rules evaluation process, site staff should verify the following on the Adverse Event form in Rave:

- The reporting period (course/cycle) is correct, and
- AEs are recorded and complete (no missing fields) and the form is query-free (fields added to the form during study build do not need to be query-free for the integration call with CTEP-AERS to be a success).

The CRA reports AEs in Rave at the time the Investigator learns of the event. If the CRA modifies an AE, it must be re-submitted for rules evaluation.

Upon completion of AE entry in Medidata Rave, the CRA submits the AE for rules evaluation by completing the Expedited Reporting Evaluation form. Both NCI and protocol-specific reporting rules evaluate the AEs submitted for expedited reporting. A report is initiated in CTEP-AERS using information entered in Medidata Rave for AEs that meet reporting requirements. The CRA completes the report by accessing CTEP-AERS via a direct link on the Medidata Rave Expedited Reporting Evaluation form.

In the rare occurrence that Internet connectivity is lost, a 24-hour notification is to be made to CTEP by telephone at [contact]. Once Internet connectivity is restored, the 24-hour notification that was phoned in must be entered immediately into CTEP-AERS using the deep link from Medidata Rave.

Additional information about the CTEP-AERS integration is available on the CTSU website:

- Study specific documents: Protocols > Documents > Education and Promotion, and
- Expedited Safety Reporting Rules Evaluation user guide: Resources > CTSU Operations Information > User Guides.

NCI requirements for SAE reporting are available on the CTEP website:

• NCI Guidelines for Investigators: Adverse Event Reporting Requirements is available at https://ctep.cancer.gov/protocolDevelopment/electronic\_applications/docs/aeguidelines.pdf.

# **10.3.2** Distribution of Adverse Event Reports

CTEP-AERS is programmed for automatic electronic distribution of reports to the following individuals: Principal Investigator and Adverse Event Coordinator(s) (if applicable) of the Corresponding Organization or Lead Organization, the local treating physician, and the Reporter and Submitter. CTEP-AERS provides a copy feature for other e-mail recipients.

# 10.3.3 Expedited Reporting Guidelines

Use the NCI protocol number and the protocol-specific patient ID assigned during trial registration on all reports.

Note: A death on study requires both routine and expedited reporting, regardless of causality. Attribution to treatment or other cause must be provided.

Death due to progressive disease should be reported as **Grade 5 "Disease progression"** in the system organ class (SOC) "General disorders and administration site conditions." Evidence that the death was a manifestation of underlying disease (e.g., radiological changes suggesting tumor growth or progression: clinical deterioration associated with a disease process) should be submitted.

# Phase 1 and Early Phase 2 Studies: Expedited Reporting Requirements for Adverse Events that Occur on Studies under an IND/IDE within 30 Days of the Last Administration of the Investigational Agent/Intervention 

#### FDA REPORTING REOUIREMENTS FOR SERIOUS ADVERSE EVENTS (21 CFR Part 312)

**NOTE:** Investigators MUST immediately report to the sponsor (NCI) ANY Serious Adverse Events, whether or not they are considered related to the investigational agent(s)/intervention (21 CFR 312.64)

An adverse event is considered serious if it results in **ANY** of the following outcomes:

- Death
- 2) A life-threatening adverse event
- 3) An adverse event that results in inpatient hospitalization or prolongation of existing hospitalization for  $\geq 24$  hours
- 4) A persistent or significant incapacity or substantial disruption of the ability to conduct normal life functions
- 5) A congenital anomaly/birth defect.
- 6) Important Medical Events (IME) that may not result in death, be life threatening, or require hospitalization may be considered serious when, based upon medical judgment, they may jeopardize the patient or subject and may require medical or surgical intervention to prevent one of the outcomes listed in this definition. (FDA, 21 CFR 312.32; ICH E2A and ICH E6).

ALL SERIOUS adverse events that meet the above criteria MUST be immediately reported to the NCI via electronic submission within the timeframes detailed in the table below.

Hospitalization	Grade 1 and Grade 2 Timeframes	Grade 3-5 Timeframes
Resulting in Hospitalization ≥ 24 hrs	10 Calendar Days	24-Hour 5 Calendar Days
Not resulting in Hospitalization ≥ 24 hrs	Not required	,

**NOTE:** Protocol specific exceptions to expedited reporting of serious adverse events are found in the Specific Protocol Exceptions to Expedited Reporting (SPEER) portion of the CAEPR.

## **Expedited AE reporting timelines are defined as:**

- o "24-Hour; 5 Calendar Days" The AE must initially be submitted electronically within 24 hours of learning of the AE, followed by a complete expedited report within 5 calendar days of the initial 24-hour report.
- "10 Calendar Days" A complete expedited report on the AE must be submitted electronically within 10 calendar days of learning of the AE.

Serious adverse events that occur more than 30 days after the last administration of investigational agent/intervention and have an attribution of possible, probable, or definite require reporting as follows:

#### Expedited 24-hour notification followed by complete report within 5 calendar days for:

• All Grade 3, 4, and Grade 5 AEs

#### Expedited 10 calendar day reports for:

• Grade 2 AEs resulting in hospitalization or prolongation of hospitalization

For studies using PET or SPECT IND agents, the AE reporting period is limited to 10 radioactive half-lives, rounded UP to the nearest whole day, after the agent/intervention was last administered. Footnote "1" above applies after this reporting period.

Effective Date: May 5, 2011

# **10.4** Routine Adverse Event Reporting

All Adverse Events must be reported in routine study data submissions. AEs reported expeditiously through CTEP-AERS must also be reported in routine study data submissions.

Adverse event data collection and reporting, which are required as part of every clinical trial, are done to ensure the safety of patients enrolled in the studies as well as those who will enroll in future studies using similar agents. AEs are reported in

a routine manner at scheduled times during the trial using Medidata Rave. For this trial the Adverse Event CRF is used for routine AE reporting in Rave.

# 10.5 Pregnancy

Although not an adverse event in and of itself, pregnancy as well as its outcome must be documented via CTEP-AERS. In addition, the *Pregnancy Information Form* included within the NCI Guidelines for Adverse Event Reporting Requirements must be completed and submitted to CTEP. Any pregnancy occurring in a patient or patient's partner from the time of consent to 90 days after the last dose of study drug must be reported and then followed for outcome. Newborn infants should be followed until 30 days old. Please see the "NCI Guidelines for Investigators: Adverse Event Reporting Requirements for DCTD (CTEP and CIP) and DCP INDs and IDEs" (at http://ctep.cancer.gov/protocolDevelopment/adverse\_effects.htm) for more details on how to report pregnancy and its outcome to CTEP.

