*Note*: Females who have undergone surgical sterilization or who have been postmenopausal for at least 2 years are not considered to be of childbearing potential.

**3.1.14** The effects of Hu5F9-G4 (magrolimab) monoclonal antibody on the developing human fetus are unknown and dinutuximab is known to be teratogenic. For this reason, female patients of childbearing potential must be willing to use one highly effective method of contraception (hormonal or barrier method of birth control; abstinence) prior to study entry, during the study and continue for 4 months after the last dose of study treatment. Should a woman become pregnant or suspect she is pregnant while she or her partner is participating in this study, she should inform her treating physician immediately.

Male patients who are sexually active with a woman of childbearing potential (WOCBP) and who have not had vasectomies must be willing to use a barrier method of contraception (condom plus spermicidal gel) and refrain from sperm donation during the study and for 4 months after the last dose of study treatment. If the partner is

pregnant, male patients must use barrier method contraception (condom) during the study and for 4 months after the last dose of study treatment to prevent fetal exposure to study treatment.

- **3.1.15** All patients and/or their parents or legally authorized representatives must have the ability to understand and the willingness to sign a written informed consent. Assent, where appropriate, will be obtained according to local institutional policy.
- **3.1.16** Cardiac Function: Cardiac ejection fraction ≥ 45% or shortening fraction ≥ 28%, no evidence of physiologically significant pericardial effusion as determined by an ECHO, MUGA or Cardiac MRI. No clinically significant ECG findings that in the judgment of the treating investigator would present a contraindication for treatment.

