- An additional hemoglobin must be checked 3 to 6 hours after the initiation of the first (Priming) and second (Week 2) doses of Hu5F9-G4 (magrolimab). The patient should be transfused as clinically appropriate. Investigators should consider additional hemoglobin monitoring during the first week of treatment in patients with symptoms of anemia or at increased risk of complications of anemia.

Men and women of reproductive potential must use effective contraception while receiving study treatment and for 4 months after the last dose of Hu5F9-G4 (magrolimab). Male patients whose partners are pregnant may continue study treatment and should use barrier method contraception (condom) to prevent exposing the fetus. Refer to Section 6.8 of for further details.

Since infusion reactions can occur, all patients should be monitored pre-priming dose (within 30 minutes), every 30 minutes (±10) during priming dose infusion, for 1-hour post-infusion of the priming dose with vital signs (heart rate, respiratory rate, blood pressure, temperature, pulse oximetry) or as clinically indicated. Vital signs and AEs will be collected 30 (±10) minutes and 1 hour (±10 minutes) post-infusion. Patients who experience any treatment-related adverse events during the observation period should be further monitored as clinically appropriate (e.g., for up to 24 hours post-dose). All patients should be monitored with hourly (±20 minutes) vital signs during and for 1-hour (±20 minutes) post-infusion for Cycle 1. Further doses (Cycle 2+) do not require post-infusion observation, but hourly (±20 minutes) vital signs during the infusion. Patients who experience any treatment-related AEs during the observation period should be further monitored as clinically appropriate.

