#### 6.8 Contraception

The effects of Hu5F9-G4 (magrolimab) monoclonal antibody on the developing human fetus are unknown and dinutuximab is known to be teratogenic.

A woman is of childbearing potential if she is postmenarcheal, has not reached a postmenopausal state ( $\geq$  12 continuous months of amenorrhea with no identified cause other than menopause), and has not undergone surgical sterilization (removal of ovaries and/or uterus).

Females of childbearing potential must have a negative urine or serum pregnancy test within 30 days of enrollment and within 72 hours prior to treatment initiation. Additional pregnancy tests (serum or urine) should be obtained throughout the study in accordance with local policy.

Female patients of childbearing potential must be willing to use one highly effective method of contraception (hormonal or barrier method of birth control; abstinence) prior to study entry, during the study and continue for 4 months after the last dose of study treatment. Should a woman become pregnant or suspect she is pregnant while she or her partner is participating in this study, she should inform her treating physician immediately.

- Examples of contraceptive methods with a failure rate of < 1% per year include: bilateral tubal ligation, male sterilization, and established proper use of hormonal contraceptives that inhibit ovulation, hormone-releasing intrauterine devices, and copper intrauterine devices.
- Hormonal contraceptive methods must be supplemented by a barrier method plus spermicide.
- The reliability of sexual abstinence should be evaluated in relation to the duration of the clinical trial and the preferred and usual lifestyle of the patient. Periodic abstinence (e.g., calendar, ovulation, symptothermal, or postovulation methods) and withdrawal are not acceptable methods of contraception.

Male patients who are sexually active with a woman of childbearing potential (WOCBP) and who have not had vasectomies must be willing to use a barrier method of contraception (condom plus spermicidal gel) and refrain from sperm donation during the study and for 4 months after the last dose of study treatment. If the partner is pregnant, male patients must use barrier method contraception (condom) during the study and for 4 months after the last dose of study treatment to prevent fetal exposure to study treatment.

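### The window for reportable pregnancies in 10.5 ends 30 to 33 days before the 4-month contraception period does; 6.5.1 covers only part of the gap, and the contraception wording also needs reconciling

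*Combined protocol and SAP*

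**What the plan says.** **Reporting.** Section 10.5 applies to any pregnancy in a patient or a patient's partner "from the time of consent to 90 days after the last dose of study drug must be reported". Such a pregnancy is then followed to its outcome, and the newborn until 30 days of age.

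**Contraception period.** Section 3.1.14 asks female patients of childbearing potential to use contraception before entry, "during the study and continue for 4 months after the last dose of study treatment". The reason it gives is that the effects of magrolimab "monoclonal antibody on the developing human fetus are unknown and dinutuximab is known to be teratogenic". Male patients have the same 4 months. Those with a pregnant partner must use a condom "for 4 months after the last dose of study treatment to prevent fetal exposure to study treatment". Section 6.8 repeats the period and the reason. Section 6.2.1.3 states the period again ("Men and women of reproductive potential must use effective contraception while receiving study treatment", and for 4 months after the last magrolimab dose), and so does 8.1.1.

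**Other notification.** Section 6.5.1 requires the investigator to tell CTEP at once of a confirmed pregnancy in a patient participating in the study. It gives no day limit and does not mention partners. Under 6.5.2, a patient who progresses on combination therapy goes off study 30 days after the last dose.

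**Which methods count.** Section 6.8 wants patients to be "willing to use one highly effective method of contraception (hormonal or barrier method of birth control; abstinence", in the same terms as 3.1.14. A few lines later it says: "Hormonal contraceptive methods must be supplemented by a barrier method plus spermicide". The note to 3.1.13 treats a woman as no longer of childbearing potential after at least 2 years postmenopausal. Section 6.8 uses at least 12 months of amenorrhea.

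**The concern.** The protocol sets a 4-month period after treatment because of possible fetal harm, yet the section that governs pregnancy reports uses a shorter one and gives no reason for the difference. A pregnancy in a partner in month 4, or in a patient who has already gone off study for progression, falls within the period in which the protocol asks for contraception but need not be reported or followed.

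Section 9.5.1 calls this a first-in-child trial, and 3.1.14 describes the fetal effects of magrolimab as unknown. Few pregnancies are to be expected, so each outcome that is not captured is a real loss of information.

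The contraception wording is a separate, smaller matter. Section 3.1 says that eligibility criteria are applied literally and without waiver. A site therefore needs one reading of who is of childbearing potential and which methods are sufficient.

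**Working it through.** There is no derived figure to reproduce, because the documents give no reasoning for the 90 days. The check is calendar arithmetic followed by a comparison of the sections.

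**Inputs**
- Reporting window after the last dose: 90 days (10.5).
- Contraception period after the last dose: 4 months (3.1.14, 6.2.1.3, 6.8, 8.1.1).
- Magrolimab terminal half-life: about 2 weeks at 10 mg/kg weekly or more (2.1.6). This is used for context only.

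The last dose is taken as the same date in every section.

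**Step 1: length of the gap.** Four calendar months, counted from every start date in 2021 to 2024, is 120 to 123 days.
- Shortest case: 120 − 90 = 30 days, and 30/120 = 25%.
- Longest case: 123 − 90 = 33 days, and 33/123 = 27%.

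**Step 2: which pregnancies in that gap are still captured.**

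| Pregnancy after day 90, within 4 months | 10.5 | 6.5.1 |
|---|---|---|
| Patient still participating | No | Notice to CTEP; no outcome follow-up stated |
| Patient off study 30 days after the last dose for progression | No | No |
| Partner of a patient | No | No |

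The first row matters. Under 6.5.2, patients who stop treatment for reasons other than progression generally stay on study until progression or the fifth anniversary of enrolment.

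**Step 3: drug remaining.** Assume simple first-order decline with a 14-day half-life.
- Day 90: 90/14 = 6.4 half-lives, and 0.5^6.4 is about 1.2%.
- Days 120 to 123: 8.6 to 8.8 half-lives, about 0.3% to 0.2%.

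This covers magrolimab only. The documents give no half-life for dinutuximab, which is the agent they call teratogenic.

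**Step 4: contraception wording.**
- A patient who uses only a hormonal method satisfies 3.1.14 and the first statement in 6.8, but not the later statement in 6.8.
- A woman with between 12 and 24 months of amenorrhea due to menopause is of childbearing potential under the note to 3.1.13 and not under 6.8.

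**The case against.** The case for leaving the text alone has several parts.

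- **The 90 days limits when a pregnancy occurs, not how long it is followed.** A reader might infer that outcome follow-up also stops at day 90. It does not: 10.5 follows a qualifying pregnancy to its outcome and the infant to 30 days of age.
- **Other rules apply after day 90.** A reader might infer that nothing does. Section 6.5.1 has no day limit for participating patients. Section 10.3.3 counts a birth defect as a serious outcome and requires expedited reporting of at least possibly related serious events beyond 30 days, with no end date. The text does not say how that rule applies to a participant's child.
- **Section 10.5 points to NCI guidelines for detail on how to report.** They are not among the documents, so what they add cannot be judged. The sentence in 10.5 still says 90 days.
- **The 4 months is a contraception period.** Nothing in the documents says that risk lasts that long or that the two windows must be equal, and on the half-life given little magrolimab remains at day 90.
- **Very few pregnancies are likely.** At most 82 patients are planned, aged 2 to 35, with contraception required throughout the gap.
- **The contraception sentences in 6.8 could be read as a general rule followed by a detail.** The postmenopausal difference hardly matters when the upper age is 35.

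Most of this stands, and it narrows the point. It does not remove it. Partners and patients off study for progression are still uncovered, 6.5.1 sets no outcome follow-up, and the protocol does not explain why reporting should end before the precaution does.

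**Conclusion.** The inconsistency is real and minor. The window in 10.5 is 30 to 33 days shorter than the protocol's own contraception period. What remains uncovered after 6.5.1 is pregnancies in partners, pregnancies in patients off study 30 days after the last dose for progression, and outcome follow-up for patients who are still participating.

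The 25% to 27% is a share of calendar time in the post-treatment contraception period. It should not be read as a share of fetal risk or of missed pregnancies. It leaves out the treatment period, and the documents give no pregnancy rate or dinutuximab half-life from which risk could be estimated.

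The conflict over hormonal methods and the two definitions of postmenopausal are also on the page. The second has little practical effect in this age range. Dose finding, sample size, error rates and efficacy analyses do not depend on any of this.

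**What to change.** 1. Reconcile the reporting window in 10.5 with the 4-month contraception period, for patients and partners, so that reporting is not shorter than the contraception period the sponsor confirms. State it in the same unit as the contraception period.
2. Align 6.5.1 with 10.5 on who is covered (patients and partners), until when, and with what outcome follow-up. Say how this applies to a patient who is already off study.
3. Reconcile 3.1.14 with 6.8 on whether a hormonal method alone is sufficient, and the note to 3.1.13 with 6.8 on postmenopausal status. Which rule and which definition are right is for the sponsor.

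The cost is one number and some aligned wording in an amendment, with very few extra reports. Patients who stop treatment without progression already have a month 4 visit under 6.6. Patients off study for progression have no scheduled visit after about day 30, so reports from them would depend on the family or treating physician making contact. That is already so for days 31 to 90 under the present 10.5.
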